
^X Assessment to be recorded in the clinical database or received electronically from a vendor
 
¹ If discontinuation, all efforts should be made to complete the EOS assessments prior to study discontinuation.
 
² S = assessment to be recorded in source documentation only
 
³ complete white blood count with differential
 
⁴ Hematology assessment at Day 2 should be performed locally before discharge of the patients; further, platelets should be closely monitored following the first week after infusion.
 
⁵ Hematology assessments at Week 4 and Week 10 are only applicable for Germany
 
⁶ HIV antibody, Hepatitis C antibody, Hepatitis B surface antigen (HBsAG)
 
█
 
█
 
⁹ HFMSE and RULM will not be administered until patient reaches 24 months of age
 
¹⁰ physical assessments may occur over the span of more than 1 day within the visit window, but must not exceed 4 days
 
█
																	

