8.5.1.2 Revised Upper Limb Module (RULM)

RULM is a validated, SMA specific assessment that measures motor performance in the upper limbs from childhood through adulthood in ambulatory and non-ambulatory individuals with SMA, and weaker individuals who have a floor effect or very low score on the Hammersmith Functional Motor Scale (HFMS) (Mazzone et al 2017). The RULM has a total of 19 scorable items: 18 items scored on a 0 (unable) to 2 (full achievement) scale, and one item that is scored from 0 (unable) to 1 (able). These item scores are summed to give a total score ranging from 0 to 37 points with lower scores reflecting poorer ability. The test is performed unilaterally using the limb preferred by the participant. The RULM will be administered by a site trained clinical evaluator (eg, licensed physical or occupational therapist, or national equivalent) in accordance with the Schedule of Assessments for all participants ≥ 24 months of age. Participants < 24 months of age at time of visit will begin having RULM assessments as such time that 24 months of age is reached.

For participants between 24-30 months of age the following two test items will not be administered and a Can Not Test (CNT) will be entered due to developmental limitations: (C)- tracing a path and (H)- tearing a paper. These items will be added into the assessment at ≥ 30 months of age.

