2.6 Analysis supporting secondary objectives

2.6.1 Secondary endpoint(s)

The secondary endpoints include:

1. Changes from baseline in HFMSE and RULM;
2. Percent of participants achieving development motor milestones according to the WHO-Multicenter Growth Reference Study (WHO-MGRS) and Bayley Scale of Infant and Toddler Development - Third Ed (Bayley-III) criteria.

For all participants of 24 months of age or more at the time of visit, HFMSE (2019 edition) will be assessed, consisting of 33 SMA-specific items with a maximal total score of 66 (O'Hagen et al 2007). Each item is scored on a 3-point Likert scale from 0 (no response) to 2 (full response) and summed up to the total score. A higher score indicates a higher ability level. A total score will not be derived if any item score is missing or "cannot test".

For all participants of 30 months of age or more at the time of visit, RULM will be assessed, consisting of 19 items with a maximal total score of 37 with lower scores reflecting poorer ability. RULM is an assessment that measures motor performance in the upper limbs from childhood to adulthood in ambulatory and non-ambulatory individuals with SMA. There are 18 items scored 0 (unable) to 2 (full achievement) and one item scored 0 (unable) to 1 (able) summed up to the total score (Pera et al 2019). For participants of 24 to 30 months of age at the time of visit, the two test items (C)- Tracing a path and (H)- Tearing Paper will not be administered and therefore for a participant between the ages of 24-30 months the maximum score achieved is 33 points. A total score will not be derived if any item score is missing or "cannot test".

Changes from baseline are only summarized for subjects whose baseline values are available. For younger subjects who are not eligible for RULM/HFMSE measure at baseline, their scores at later visits will only be listed.

The Developmental Milestone Checklist consists of 10 Developmental Motor Milestones obtained from WHO-MGRS (sitting without support, hands-and-knees crawling, standing with assistance, walking with assistance, standing alone, and walking alone) and from Bayley-III (head control (Bayley gross motor item #4), sits with slight support for at least 30 seconds (Bayley gross motor item #19), sits without support for at least 30 seconds (Bayley gross motor item #26), and pulls to stand (Bayley gross motor item #35)) (WHO Multicentre Growth Reference Study Group 2006, Bayley 2006).

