2.6.2 Statistical hypothesis, model, and method of analysis

No hypothesis testing will be performed.

The secondary endpoints will be summarized by weight bracket and overall for the FAS.

For all participants of 24 (HFMSE) or 30 (RULM) months of age or more at baseline, changes from baseline in HFMSE and RULM will be summarized descriptively; in addition, mixed models with repeated measurement will be fitted that include the change from baseline as the dependent variable, and fixed effects of weight bracket, visit, and their interaction as well as covariate of baseline value. The least squares means and 95% 2-sided confidence intervals will be reported for each visit. Changes in total scores over time will be visualized by means of box-whisker plots and individual longitudinal trajectories. The number and proportion of participants with increases and with decreases in total scores compared to baseline (any, by more than 3, 6, 10 points inclusive) will be presented by visit and weight bracket.

The number and proportion of participants achieving each developmental motor milestone will be presented per visit by weight bracket and overall. In addition, summaries of achievements respective to baseline achievement status will also be generated separately.

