2.6.5 Sensitivity analyses

For HFMSE and RULM, in a sensitivity analysis of change in total score from baseline, on any missing data due to SMA-related death or invasive ventilation the HFMSE and RULM total scores will be set to 0, and on any missing data due to death for other causes to the last observed total score before death.

In further sensitivity analyses of changes from baseline in HFMSE and RULM total scores, missing item scores and “cannot test” assessments will be imputed by 0 scores for analysis. This applies as long as no more than 6 (HFMSE) and 3 (RULM) item scores per visit are missing or “cannot test”. If more items are missing or “cannot test”, total scores are not derived.

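### Does scoring cannot-test RULM items as 0 in SAP 2.6.5 create a spurious gain for children who pass 30 months of age?

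*SAP*

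**What the plan says.** **How the test is given.** Footnote 9 to Protocol Table 8-1 states that "HFMSE and RULM will not be administered until patient reaches 24 months of age". Protocol 8.5.1.2 adds that between 24 and 30 months "the following two test items will not be administered and a Can Not Test (CNT) will be entered"; the items are C (tracing a path) and H (tearing paper). It continues: "These items will be added into the assessment at ≥ 30 months of age".

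**How the total is formed.** SAP 2.6.1 begins: "For all participants of 30 months of age or more at the time of visit, RULM will be assessed". It then describes the 24-30 month case, where "the maximum score achieved is 33 points. A total score will not be derived if any item score is missing"; a cannot-test item has the same effect. The same section summarises change only where a baseline value exists. For children too young for the measure at baseline, it only lists later scores.

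**Who is analysed.** SAP 2.6.2 opens: "For all participants of 24 (HFMSE) or 30 (RULM) months of age or more at baseline, changes from baseline in HFMSE and RULM" are summarised and modelled. It also counts those "with increases and with decreases in total scores compared to baseline (any, by more than 3, 6, 10 points inclusive").

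**The sensitivity analysis.** SAP 2.6.5 covers changes from baseline in the two total scores. Its rule for missing and cannot-test items is: "assessments will be imputed by 0 scores for analysis. This applies as long as no more than 6 (HFMSE) and 3 (RULM) item scores" (counted by visit). Above that limit no total is formed.

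**The concern.** Two designed cannot-test items fit under the RULM limit of three. Taken literally, 2.6.5 therefore gives a child of 24-30 months a baseline total that the main rule withholds, with two items that were never offered counted as failures. Once the child passes 30 months the items are given, and whatever the child scores on them appears as improvement. Children only get older, so the shift can only go towards benefit, and there is no control group in which the same shift would cancel.

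The 33-point sentence in 2.6.1 sharpens the worry. Under the main rule a child with C and H recorded as cannot test never gets a total, so a 33-point maximum could become a usable total only through 2.6.5. A programmer might take that as a sign that 2.6.5 is meant for this age group.

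**Working it through.** **1. Reproduce the stated maxima.** Inputs from SAP 2.6.1: 18 items scored 0-2 and one scored 0-1.

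- Full maximum: 18 × 2 + 1 × 1 = 37, as stated.
- Without C and H: 37 - 2 × 2 = 33, as stated. Both withheld items are therefore 0-2 items.

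**2. Size if 2.6.5 were applied to a child of 24-30 months.**

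- Limit check: 2 designed cannot-test items ≤ 3, so a total would be formed.
- Later contribution of C + H, each 0, 1 or 2: 0, 1, 2, 3 or 4 points. The artefact is 0 to +4 per child and never negative. The full +4 needs a score of 2 on both items.

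**3. When it would appear.** Baseline RULM is at Screening Visit 2 (Day -15) and Week 26 is Day 183.

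- Day -15 to Day 1 (no Day 0): 15 days. Day 1 to Day 183: 182 days. Sum: 197 days.
- At 30.4375 days per month (SAP 2.3.2): 197 / 30.4375 = 6.47 months.
- A child aged 24.0 months at baseline is then 24.0 + 6.47 = 30.47 months old. On nominal days every such child has passed 30 months by Week 26, so both the 6- and 12-month changes would be exposed.

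**4. Does the SAP let such a child in?** Setting the rules side by side by age at the baseline RULM:

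| Age at baseline RULM | C and H at baseline | Main total (2.6.1) | In RULM change analysis (2.6.2) | Artefact |
|---|---|---|---|---|
| under 24 months | RULM not given | none | no; later scores listed | none |
| 24 to under 30 months | withheld, cannot test | none | no | 0 to +4 only if 2.6.5 is applied outside the 2.6.2 population |
| 30 months or more | given | formed if complete | yes | 0 |

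The exposed row is the one that 2.6.2 leaves out. Section 2.6.5 names no new endpoint and no new population. It varies the handling of incomplete item scores for the changes defined in 2.6.2, and the ordinary reading is that everything else stays fixed.

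**5. Is the 30-month limit deliberate?** Footnote 9 starts both scales at 24 months, yet 2.6.2 uses 24 months for HFMSE and 30 for RULM. The only reason the documents offer for that difference is the withholding of C and H before 30 months. I infer that the limit was set to keep these children out of the change scores.

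**The case for a change.** The strongest case is that 2.6.5 does not itself state the age limit, while other text could be read against it.

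- *The 33-point sentence and footnote 9.* Both show that children of 24-30 months are tested, so they are arguably eligible at baseline and not covered by the listing-only rule. The tension is real: 2.6.1 sets assessment from 30 months and then describes a younger version. But those texts describe the instrument and its administration. The explicit rule on who enters a change analysis is in 2.6.2, and SAP section 1 puts the SAP above the protocol on statistical matters.
- *SAP 2.6.3 uses all available data except data after prohibited medication.* That is a rule for intercurrent events, not a population definition. If it overrode the age limit in 2.6.5, it would override it in the main analysis too.
- *The date at which age is taken.* SAP 2.3.2 computes age at infusion. A child turning 30 months in the 15 days (13-17 with the visit window) after Screening Visit 2 might pass the limit with C and H recorded as cannot test. That is 15 / 182.6 = 8.2% of the six-month age band by length. However, 2.3.2 concerns the demographic summary and is not linked to the 2.6.2 limit. SAP 2.1.1 defines baseline as the last measurement before infusion, which for RULM is the Screening Visit 2 test, and 2.6.1 speaks of age at the visit. It stands only that 2.6.2 does not spell the date out.
- *Small groups.* If *k* children were wrongly included among *m* with a RULM change, a raw mean would move by up to 4*k*/*m*. Assuming one such child in a weight bracket where all 6 to 10 planned participants contribute, that is 4/10 = 0.40 to 4/6 = 0.67 points. Neither *k* nor *m* is in the documents. *k* may be 0, and *m* is below the enrolled number if any child is under 24 months at baseline. The effect on least squares means adjusted for baseline has not been worked out. The change categories in 2.6.2 (any change, then 3, 6 and 10 points) are not said to be repeated in 2.6.5.

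What stands is a missing cross-reference and one awkward sentence.

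**Conclusion.** No change to the plan follows. With the SAP read as a whole, the RULM sensitivity analysis covers children of 30 months or more at their baseline RULM. All 19 items are given to them throughout, and the artefact is 0 points. This rests on two assumptions: that the 2.6.2 population carries over to 2.6.5, and that age is taken at the baseline RULM assessment. Both are the ordinary reading, and neither is written out in 2.6.5.

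Only if an analyst departed from that population could an affected child gain 0 to +4 points on passing 30 months, and the number of such children is unknown. Even then the effect would stay within one sensitivity analysis of a descriptive secondary endpoint with no hypothesis test. The main RULM analysis is protected twice, by the age limit and by the rule that no total is formed when any item is cannot test. A cross-reference would make the text tidier but, on the ordinary reading, would not alter any result.

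### SAP 2.6.5 scores untested HFMSE and RULM items as 0 at baseline as well as at follow-up, so the direction of this change-from-baseline sensitivity analysis is uncontrolled

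*SAP*

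**What the plan says.** The main analysis is strict about incomplete tests. SAP 2.6.1 states: "A total score will not be derived if any item score is missing", and treats an item marked as not testable the same way. It summarises change only for children who have a baseline value.

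SAP 2.6.5 relaxes this. The passage opens "In further sensitivity analyses of changes from baseline in HFMSE and RULM total scores" and says that missing items and cannot-test "assessments will be imputed by 0 scores for analysis". The limit is "This applies as long as no more than 6 (HFMSE) and 3 (RULM) item scores per visit are missing" or not testable; beyond that no total is derived. The rule is not restricted to post-baseline visits, and no separate baseline rule is given. The section states neither a purpose nor an intended direction.

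Three other provisions bear on the point:
- Protocol Table 8-1 schedules HFMSE and RULM once before dosing, at Screening Visit 2.
- SAP 2.1.1 defines change as the later value minus the baseline value, and uses one baseline throughout.
- SAP 2.6.2 fits a repeated-measures model to the change, with the baseline value as a covariate.

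**The concern.** Zero is the lowest item score, but its effect on a change score depends on the visit. At follow-up it pulls the change down. At baseline it lowers the reference point and pushes the change up. An item not tested at Screening Visit 2 and scored 2 at Week 26 shows a 2-point gain even if the child could have done it before dosing.

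The baseline case carries particular weight here. With one scheduled pre-dose assessment, no second test is planned that could supply a complete baseline. A child with one untested baseline item has no baseline total in the main analysis, and so enters the change analyses only through this rule, with zeros in the baseline. A follow-up gap affects one visit; a baseline gap affects all five efficacy visits (Weeks 4, 13, 26, 39 and 52).

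A sensitivity analysis is useful if one knows which way it leans. If this one agrees with the main result, or differs from it, the reader cannot tell how much comes from the children and how much from where the gaps happened to fall.

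**Working it through.** **Inputs**

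| Input | Value | Source |
|---|---|---|
| HFMSE items, item range | 33, 0 to 2 | SAP 2.6.1 |
| RULM items, item range | 18 at 0 to 2, one at 0 to 1 | SAP 2.6.1 |
| Most items imputed per visit | 6 HFMSE, 3 RULM | SAP 2.6.5 |
| Change categories | 3, 6, 10 points | SAP 2.6.2 |
| Children | 6 to 10 per bracket, 24 to 30 overall | SAP 1.1 |

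**The plan's own maxima.** HFMSE: 33 x 2 = 66, matching "consisting of 33 SMA-specific items with a maximal total score of 66". RULM: 18 x 2 + 1 = 37, and without the two items withheld at 24 to 30 months 37 - 4 = 33. Both agree with SAP 2.6.1.

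**Formula.** Let b and f be the scores an item would have received at baseline and at the visit had it been tested. Then

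analysed change = true change + (sum of b over items zeroed at baseline) - (sum of f over items zeroed at the visit).

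The first sum is never negative, so baseline zeros can only raise the change. The second is subtracted, so follow-up zeros can only lower it.

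**Bounds per child**
- HFMSE: 6 x 2 = 12, so -12 to +12, or 12/66 = 18% of the scale in either direction.
- RULM: 3 x 2 = 6, so -6 to +6, or 6/37 = 16%.
- Same items untested at both visits, same ability on them: the two sums cancel.
- Child truly unable at baseline: b = 0, and the baseline zero adds nothing artificial.

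A simulation of 100,000 HFMSE item sets with no true change and 0 to 6 untested items at each visit reached +12 and -12 and went no further.

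**Against the reported categories.** Take a child with no true change who would score 2 on the untested items, with gaps at baseline only:

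| Untested HFMSE items at baseline | Artificial change | Highest category reached |
|---|---|---|
| 1 | +2 | none |
| 2 | +4 | 3 |
| 3 | +6 | 6 |
| 5 | +10 | 10 |
| 6 | +12 | 10 |

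The categories serve here as a yardstick; SAP 2.6.5 does not say whether the category counts are repeated under this rule. The signs reverse if the gaps are at follow-up only.

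**On a raw mean.** One child at the +12 extreme moves a bracket mean by 12/10 = 1.2 to 12/6 = 2.0 points, and the overall mean by 12/30 = 0.4 to 12/24 = 0.5, if every enrolled child contributes. The documents give no rate of untested items, so no expected mean effect can be calculated.

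**With zeros after baseline only and a complete baseline required.** The first sum vanishes and the HFMSE range becomes -12 to 0.

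**The case against.** **The distortion runs both ways.** This is correct. It is why the finding is uncontrolled direction and not upward bias. A reader might infer a net inflation of the mean, but the documents do not support that. They do not say how often items go untested at either visit, and treating every later point on such an item as spurious would count real improvement as error.

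**The plan does not call this analysis conservative.** Also correct. A reader might infer that intention from the choice of the lowest score, but SAP 2.6.5 states no purpose, so the SAP cannot be said to miss a stated aim. The point does not need that claim.

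**A cannot-test item may reflect inability, so 0 may be right.** This stands in part. However, inability already has its own score of 0, and Protocol 8.5.1.2 enters cannot-test for two RULM items withheld because of age. The code therefore does not by itself mean inability.

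**Safeguards exist.** Table 8-1, footnote 10, lets testing spread over up to 4 days within the visit window. Protocol 8.5.1.1 describes the HFMSE as designed with fatigue in mind and given by trained evaluators. SAP 2.1 lists all individual data. These make six untested items in one child unlikely, but they do not exclude two or three.

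**The model adjusts for baseline.** The imputed zeros sit in both the covariate and the change score, so adjustment does not reliably remove the distortion, and the descriptive summaries are unadjusted.

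**Little rests on the result.** This stands and limits the weight of the point: the endpoints are secondary, descriptive and untested, and no decision rule uses this output. Nor is this the only place where a child with gaps is kept. A child with a complete baseline and one incomplete follow-up test remains in the main model at the other visits.

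**Conclusion.** The point holds with limited reach. As written, the rule imputes 0 at baseline as well as afterwards, and the two act in opposite directions on change. Per child the artefact lies between -12 and +12 HFMSE points and between -6 and +6 RULM points. Those are extremes: they need the maximum number of untested items, all at one visit, in a child able to score 2 on each. Two HFMSE items untested at baseline are enough to pass the 3-point category.

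This rests on reading the unrestricted wording as covering baseline, which the SAP never names, and on the single scheduled pre-dose test. The main analysis is unaffected because it derives no incomplete totals.

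A related RULM case needs clarifying but is not required for the conclusion. For the youngest tested children, SAP 2.6.1 says that "for a participant between the ages of 24-30 months the maximum score achieved is 33 points". SAP 2.6.2 limits the RULM change analysis to those at least 30 months old at baseline, and SAP 2.6.5 does not say whether that limit carries over. If it does not, the two withheld items fall within the limit of 3, and a child passing 30 months during follow-up could gain up to 2 x 2 = 4 points because the items were added.

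**What to change.** In SAP 2.6.5:
1. Apply the 0 score to post-baseline visits only.
2. Require a fully scored baseline total, which also serves as the model covariate.
3. Keep the limits of 6 and 3 items per visit.
4. Report by visit and weight bracket how many children had items imputed.

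The artefact then has one known direction: the largest artificial HFMSE gain falls from +12 to 0, and the largest artificial loss stays at -12.

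If children with an incomplete baseline are to be kept, show them in a separate run, with change computed over the items scored at baseline and the covariate defined on the same items. Without that last step the model covariate is undefined for them.

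The cost is a few SAP sentences and some item-level programming; item-level data are already needed to apply the 6 and 3 limits. The downside is that children with an incomplete baseline leave the modified analysis, or appear separately on a reduced item set that is not comparable with the full 66- or 37-point scale.

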2.6.6 Supplementary analyses

No supplementary analysis is planned.

2.7 Safety analyses

Safety will be assessed through the incidence and severity of AEs, vital sign assessments, cardiac assessments, laboratory evaluations (chemistry, hematology, immunology, urinalysis), physical and neurological examinations, and use of concomitant medications. Adverse events will be coded in accordance with the most current version of the MedDRA coding dictionary. Safety assessments will be presented in data listings or patient profiles for the safety population.

Safety is the primary objective of the study. Summary of adverse events, vital signs, and clinical laboratory results are described in Section 2.5. Summaries will be presented per weight bracket and overall.

